Participants will be selected from the Maxillofacial and Plastic Surgery Department, Faculty of Dentistry, Alexandria University, Egypt.

Sample size calculation

The size was estimated based on 5% alpha error and 80% study power. The mean (SD) improvement in Maximum Interincisal Opening (MIO) after 6 months compared to the preoperative measurements was 6.09 (7.05) mm for Level I arthroscopy, (10) 6.7 (5.25) mm for Level II arthroscopy, ⁽²⁷⁾ and 18.5 (2.1) mm for Level III arthroscopy. ⁽²⁸⁾ Based on difference between independent means using F test and pooled SD = 4.8 mm, the minimum sample size was calculated to be 9 joints per group, increased to 10 joints to make up for lost to follow up cases. Total sample = number per group x number of groups = 10 x 3 = 30 joints. Sample size was based on Rosner's method ⁽²⁹⁾ calculated by G*Power 3.1.9.7. ⁽³⁰⁾

Randomization

Participants will be randomly assigned using online program (www.random.org) in order to allocate participants to the group.

Allocation Concealment

Sequentially numbered opaque sealed envelopes will be used to conceal allocation. One set of envelopes will be created to guarantee they were opaque, sealed and sequentially numbered.

Blinding

The patients will be blinded to the treatment group.

Intervention

Group I: 10 patients will be treated with level (I) arthroscopy (Lysis and lavage).

Group II: 10 patients will be treated with level (II) arthroscopy (operative arthroscopy).

Group III: 10 patients will be treated with level (III) arthroscopy (operative arthroscopy + disc repositioning and fixation).

Eligibility Criteria

Inclusion criteria

The patients with TMJ internal derangement will be divided into 5 stages according to Wilkes Classification.⁽¹¹⁾ Only patients with stage III will be

included in this study.

Exclusion criteria

1. Medically unfit patients.
2. Patients with TMDs secondary to malocclusion.
3. Psychological instability.
4. Patients operated before for other TMJ problems.

Materials

In all procedures, 1.9 mm, 30-degree optical device, sleeves, sharp and blunt trocars, adhesion knives, an exploratory probe, a bipolar electrode (Karl Storz Endoscopy, Tuttlingen, Germany) and coblator.

A specific material for pin placement is A third custom-made cannula (2.7mmdiameter) with a distal parallel double window (10 _ 2 mm) for direct view control of pin fixation, a long 1.5-mm rotatory drill for perforating disc and condyle, and an impactor with hammer (fixation kit).

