2. Short hospital stay with early recovery and rapid return to work.

The risks to the participant and/or the community

1. The need for long-term follow-up postoperative.
2. The exposure to radiation in MRI which is needed for follow-up at 6 months.

Anonymity and Confidentiality

The anonymity and confidentiality of the participants will be preserved by not revealing their names and identity in the data collection, analysis and reporting of the study findings.

The identity of participants will be kept confidential or anonymous and the assurances extend beyond protecting their names to also include the avoidance of using self-identifying statements and information.

DATA MANAGEMENT & STATISTICAL ANALYSIS

Data will be collected and analyzed statistically using ANOVA test to compare between the three groups.

REFERENCES

2. Thapliyal GK. Peterson's Principles of Oral & Maxillofacial Surgery. *Med J Armed Forces India.* 2006;62(1):89-.

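### The stated minimum of 9 joints per group does not follow from the stated inputs, which give 4; the trial is not undersized for its overall F test

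*Combined protocol and SAP*

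**What the plan says.** The section on sample size calculation sets the error rates: "The size was estimated based on 5% alpha error and 80% study power". It bases the calculation on the 6-month improvement in maximal interincisal opening and takes a mean (SD) for each arm from a separate published source:

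- "6.09 (7.05) mm for Level I arthroscopy"
- "6.7 (5.25) mm for Level II arthroscopy"
- "18.5 (2.1) mm for Level III arthroscopy"

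The method is an F test comparing the group means, and the SD and the result are given as "pooled SD = 4.8 mm, the minimum sample size was calculated to be 9 joints per group". Nine is then raised to 10 to allow for losses, giving 30 joints in total, with G*Power named as the software. The paragraph reports no effect size f, no sample sizes for the source studies and no multiplicity adjustment.

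The planned analysis matches the sizing test. Under data management and statistical analysis the protocol says: "Data will be collected and analyzed statistically using ANOVA test to compare between the three groups".

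**The concern.** The paragraph supplies everything a one-way ANOVA sample size needs, so anyone can rerun it. The assumed Level III gain exceeds the other two by 11.8 and 12.4 mm, against an SD of 4.8 mm. An effect that large should need very few joints per group, and 9 looks too many for 80% power. The SD also looks wrong: 4.8 is what one gets by averaging the three SDs directly, which is not how SDs are pooled.

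This paragraph is the only justification for the size of a surgical trial. If its result contradicts its inputs, then either an input or the result is misreported, and an ethics committee or a reader cannot tell which, or what effect the 9 was meant to detect. A priori the error could also have hidden a shortfall in power, so its direction had to be checked.

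**Working it through.** **Inputs** (all from the sample size section): means 6.09, 6.7 and 18.5 mm; SDs 7.05, 5.25 and 2.1 mm; SD used 4.8 mm; alpha 0.05; power 0.80; three equal groups; F test.

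**Step 1. Try to reproduce 9 from the stated inputs.**

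- Grand mean = (6.09 + 6.7 + 18.5)/3 = 10.43 mm.
- Deviations are −4.34, −3.73 and 8.07; their squares sum to 18.84 + 13.91 + 65.12 = 97.87.
- SD of the means = √(97.87/3) = 5.712 mm.
- f = 5.712/4.8 = 1.190.
- Power comes from the noncentral F distribution with 2 and 3n − 3 degrees of freedom and noncentrality 3n·f².

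| Joints per group | Power at SD 4.8 mm |
|---|---|
| 3 | 68.7% |
| 4 | 88.0% |
| 5 | 95.9% |
| 9 | 99.97% |

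The minimum for 80% is 4 per group (12 in total), not 9 (27 in total).

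**Step 2. Check the SD.** (7.05 + 5.25 + 2.1)/3 = 14.4/3 = 4.80 exactly. Pooling averages variances. With equal weights, √((49.70 + 27.56 + 4.41)/3) = √27.23 = 5.22 mm. Equal weights are an assumption, because the source sample sizes are not given.

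**Step 3. See whether any pooled SD gives 9.** Whatever the weights, a pooled SD lies between the smallest and largest of the three.

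| Common SD (mm) | f | Minimum per group for 80% | Power at that n | Power at 9 per group |
|---|---|---|---|---|
| 2.1 | 2.72 | 2 | 90.9% | >99.9% |
| 4.8 | 1.19 | 4 | 88.0% | 99.97% |
| 5.22 | 1.09 | 4 | 81.9% | 99.87% |
| 7.05 | 0.81 | 7 | 87.2% (79.9% at 6) | 95.2% |

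**Step 4. Find the SD that would give 9.** Power is exactly 80% at f = 0.682 with 8 per group and at f = 0.637 with 9. These correspond to SDs of 5.712/0.682 = 8.38 mm and 5.712/0.637 = 8.97 mm. Nine is therefore the minimum only for an SD between about 8.4 and 9.0 mm, above every SD cited.

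**Step 5. Other readings at SD 4.8 mm and 80% power.**

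- Alpha of 0.05/3 gives 5 per group.
- A pairwise t test of Level III against Level I or Level II gives 4; with Bonferroni, 5 and 6 respectively.
- Simulating the ANOVA with the three unequal SDs gives about 85% power at 4 per group and over 99.9% at 9.
- SD 7.05 mm with 95% power does give 9, but the paragraph states 4.8 mm and 80%.

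**Step 6. What 9 per group can detect.** If one level differs from the other two by Δ, the SD of the means is Δ√2/3, so Δ = 0.637 × SD × 3/√2 at 80% power. This is 6.5 mm for SD 4.8 and 7.0 mm for SD 5.22, with a range of 2.8 to 9.5 mm for SDs from 2.1 to 7.05.

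**Step 7. Level I against Level II.** The assumed difference is 6.7 − 6.09 = 0.61 mm. A two-sample t test with 9 per group has 5.7% power at SD 4.8 (5.3% at SD 7.05, 8.9% at SD 2.1).

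**The case against.** The strongest reply is that nothing depends on the error. Nine exceeds the requirement at every cited SD, and no enrolment, analysis or decision changes. That is right about the consequences, and it is why the remedy is confined to wording. It does not make the stated minimum correct.

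Second, 4.8 mm might be a genuine pooled SD with unequal weights. With the source sample sizes missing, this cannot be excluded; the exact match to the plain average is suggestive, not proof. This point stands, but it does not help the 9: at 4.8 mm as written, the minimum is 4.

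Third, 9 may have been a total misread as a per-group figure. If f is built from the n − 1 SD of the three means, f = 1.46 and 3 per group gives 85.4% power (45.8% at 2). A repeated-measures between-group test, assuming a correlation of 0.5, also passes 80% at 3 per group (81.0% with two measurements, 85.4% with three). Either is a possible history of the error, but neither is documented, and neither makes 9 per group the minimum. They do limit the 8.4 to 9.0 mm statement to a per-group reading at a single time point.

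Finally, calling the error conservative holds only for the overall test on mouth opening under the cited means. The protocol lists five primary aims and sizes one. That limit is accepted.

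**Conclusion.** The concern holds. The stated inputs give 4 joints per group for 80% power, and no pooling of the cited SDs gives more than 7. The published minimum of 9 is therefore not reproducible as written. The 4.8 mm is very probably an average of SDs mislabelled as pooled, but it does not explain the 9.

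This is a wrong stated figure, not an undersized trial. For the overall ANOVA on mouth opening, 9 evaluable joints per group give at least 95% power under the cited means at every SD quoted. That rests on the assumed means, above all the Level III gain of 18.5 mm, and on a common SD no larger than 7.05 mm. It does not extend to the other primary aims or to the Level I versus Level II comparison. It should be corrected, because the paragraph alone justifies the sample size.

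**What to change.** Keep 10 per group and rewrite the paragraph in one of two ways.

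1. Report the G*Power inputs that actually produced 9: f, SD and how it was pooled, alpha and power. If source sample sizes were used as weights, give them and the resulting SD.
2. If those inputs cannot be recovered, withdraw the claim that 9 is the minimum for 80% power and replace it with reproducible text, for example:

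> Taking the cited means, 5% alpha and a common SD of 5.22 mm (square root of the mean of the three variances, equally weighted), f = 1.09 and a one-way ANOVA F test requires 4 joints per group for 80% power. We will enrol 10 per group and expect 9 to be evaluable. Nine per group gives more than 99% power under the cited means (95% if the SD is 7.05 mm) and about 80% power if one level differs from the other two by 7 mm.

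The 7 mm describes what the chosen size can detect; the documents give it no clinical standing.

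A separate sentence is worth adding: power for the assumed 0.61 mm difference between Levels I and II is only about 6%, so a non-significant result there must not be read as equivalence. This follows from the small assumed difference, not from the 9 or the 4.8.

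The cost is one rewritten paragraph. Enrolment, design and analysis are unchanged.

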According to Murakami on the rationale of arthroscopic surgery of the TMJ, he stated that, although various arthroscopic disc repositioning and suturing techniques were reported, the success rate was comparable to arthroscopic lysis and lavage, and the documentation by postoperative imaging was insufficient.⁽²⁴⁾

According to Israel: Numerous intra-articular operative arthroscopic techniques have been reported in the literature since the advent of temporomandibular joint (TMJ) arthroscopy. However, Ideal randomized controlled trials regarding outcomes are lacking nor are their strong evidence supporting one operative technique over another.⁽¹⁵⁾

Nowadays, minimally invasive procedures have eliminated the use of many of the more complex surgical procedures. Despite such advancements, however, clinicians are still encountering some difficulty in successfully treating many of these patients and finding the answers to these problems will

depend on future developments.

A review of the literature reveals that there is lack of randomized clinical trials to compare between the three levels of TMJ arthroscopy in the management of TMJ internal derangement.

The null hypothesis states that there will be no significant difference between the three levels of TMJ arthroscopy. Consequently, by doing the necessary studies and comparing the results, we can accept or reject this theory to finally develop guidelines and standardized patient selection criteria that can be followed by all researchers.

AIM OF THE STUDY

To compare between the three levels of TMJ arthroscopy in the management of TMJ internal derangement in the following points:

Primary aims are to assess:

1. Pain score using the visual analog score (VAS).⁽²⁵⁾
2. Presence or absence of clicking.
3. Mouth opening measuring the maximal interincisal opening in MIS.
4. Lateral excursion movement.
5. Protrusive movement.

[figure not shown]
Secondary aims are to assess:

1. Operative time.
2. Post operative MRI (disc position).

CONSORT

TRANSPARENT REPORTING of TRIALS

Study design

This study will be a randomized controlled clinical trial, with 1:1:1 ratio and will be reported according to CONSORT guidelines ⁽²⁶⁾

PICO Question

Do patients with TMJ internal derangement treated with arthroscopy level I compared to arthroscopy level II or arthroscopy level III show better maximal interincisal opening and less pain?

Settings and Location:

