Resorbable pins are Smart Nail (ConMed, Linvatec, Tampere, Finland), 1.5mm _ 16mmsize (head of pin 2.5mm in diameter and flange of 1 mm) and manufactured of polylactic acid copolymer (Self-Reinforced 96L/4D PLA). The mean degradation period was standardized between 18 and 26 months. ⁽³¹⁾

Pre-surgical evaluation

All patients will be subjected to full history taking, full clinical examination and investigations including preoperative MRI and Panoramic x-ray to assess the dental condition.

Surgical technique

- 1- All procedures will be done under general anesthesia (nasotracheal intubation).**
- 2- The triple-channel arthroscopic technique of McCain et al is used⁽³²⁾**

After the first puncture of the fossa, a systematic diagnostic arthroscopy is carried out. A second puncture is carried out aiming at the anterior recess under direct arthroscopic visualization (Level I).

3- Anterior release: (*Level II*)

Through the working cannula additional local anesthesia is injected to avoid post-operative pain and to decrease bleeding; it can also reduce the risk of masticatory muscle nerve injury. A Knife, coblation or laser probe are used to cut the anterior attachment of the disc and the neighboring part of the lateral pterygoid muscle. The incision line is located approximately 2–3 mm anterior to the anterior band of the disc and is

carried out across the whole width from medial to lateral. The depth of the anterior release is no more than 2 mm to avoid breaking large blood vessels and damaging the masticatory muscle nerve in the anteromedial synovium.

5- Retrodiscal scarification or contracture

Retrodiscal tissue is contracted using bipolar cautery, laser, or coblation. The target area of the retrodiscal contracture is generally the boggy and redundant synovium found lateral to the oblique protuberance. Contracture is visible during the procedure, but the most significant contracture occurs 2 to 3 weeks postoperatively as the scar thickens. The purpose of the contracture is to enhance the posterior positioning of the disc and hold it there. The posterior synovectomy and the scar contracture are also done to reduce volume of the joint space so the disc can sit more posteriorly.

6- Disc reduction

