After the anterior release is completed, the obturator is positioned at the anterior margin of the disc and the disc is pushed backwards. The obturator slides along the surface of the disc and arrives in the posterolateral recess. The retrodiscal tissue is pushed down inferiorly and posteriorly.

7- Disc fixation: (Level III)

A disc fixation can be accomplished in 1 of 2 ways. The first and more traditional way is the suture discopexy. A second way is by rigid fixation with either resorbable or titanium screws. Regardless of the methodology of fixation, the disc is held in reduction during the course of the fixation. The target area of fixation is the posterior lateral corner of the disc-condyle assembly, the area of the lateral pole where the disc attaches to the condyle.

Postoperative management

Antibiotics and nonsteroidal anti-inflammatory drugs are routinely prescribed for 5 days. The softness of the postoperative diet should be decreased slowly. Exercises to improve mouth opening are explained to the patient and start 1 week after operation.

In patients with significant postoperative occlusal changes, a splint is recommended. It is designed to raise the bite and prevent contact between upper and lower incisors and canines. Due to the resulting distalization of the bite force, joint loading is reduced, which contributes to the joint's rehabilitation. The appliance should be left in place around the clock during the first ten postoperative days, then used at night for four additional weeks.⁽³⁴⁾

Follow up

- Pain assessment using VAS (Visual Analogue Scale) ⁽²⁵⁾

- Clicking (improvement or persistence).
- Range of motion ⁽³³⁾ including: maximal interincisal opening, lateral excursion movement and Protrusive movement
- Post-operative MRI at 6 months for detection of disc position.
- All patients will be followed up at 1, 3, 6 months.

ETHICAL CONSIDERATIONS

Research Ethics Committee approval

The research protocol will be approved by the Research Ethics Committee of Alexandria University Faculty of Dentistry (IRB No. 001056 – IORG 0008839) prior to any research-related activities

All research activities involving human subjects will abide with the Declaration of Helsinki ⁽³⁴⁾ and other ethical guidelines adopted by the Research Ethics Committee of Alexandria University Faculty of Dentistry.

The benefits to the participant and/or the community

1. Treatment of patients with internal derangement with minimally invasive surgery (TMJ arthroscopy).

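### Blinding covers patients only: nothing masks whoever measures jaw movement, scores clicking or reads the 6-month MRI, so these outcomes can be scored with knowledge of the arm

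*Combined protocol and SAP*

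**What the plan says.** All places are in the combined protocol and SAP.

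- **Blinding** consists of one sentence: "The patients will be blinded to the treatment group". No assessor, MRI reader or analyst is mentioned.
- **Allocation Concealment** is a separate provision: "Sequentially numbered opaque sealed envelopes will be used to conceal allocation". It protects the assignment step and does not mask anyone who records outcomes later.
- **Aim of the study** lists five primary aims: VAS pain, "Presence or absence of clicking", "Mouth opening measuring the maximal interincisal opening in MIS", lateral excursion and protrusion. MRI disc position is a secondary aim.
- **Follow up** repeats these as "Clicking (improvement or persistence", as range of motion ("maximal interincisal opening, lateral excursion movement and Protrusive movement") and as "Post-operative MRI at 6 months for detection of disc position". Visits are at 1, 3 and 6 months. It does not say who measures, scores or reads.
- **Settings and Location** names the department and gives no staff, roles or numbers.
- **Data management & statistical analysis** plans an ANOVA across the three groups.

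**The concern.** Patient blinding protects the patient-rated VAS. It does not by itself protect what another person records. Three primary outcomes (MIO, lateral excursion, protrusion) are measurements that an examiner would ordinarily take. Clicking is a fourth if the examiner detects it, and MRI disc position needs a reader.

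MIO matters most, because both the sample size and the PICO question rest on it. Maximal opening depends partly on effort and encouragement. Scoring clicking as improved or persistent is a judgement against an earlier state. Disc position is the feature that Level III surgery sets out to change, so a reader who knows that a disc was fixed has an expectation before opening the images.

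The Introduction cites the view that imaging documentation after disc repositioning has been insufficient, and the trial aims to inform guidelines. Bias entering at measurement cannot be removed in the analysis.

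**Working it through.** **1. Who is masked, outcome by outcome**

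| Outcome | Recorded by, according to the plan | Masking stated |
|---|---|---|
| VAS pain (primary) | the patient, by the nature of the scale | yes, patient |
| Clicking (primary) | not stated | only if patient-reported |
| MIO (primary) | not stated | none for a measurer |
| Lateral excursion, protrusion (primary) | not stated | none for a measurer |
| MRI disc position (secondary) | not stated | none for a reader |

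Three of the five primary outcomes, four if clicking is examiner-detected, have no stated masking of the person recording them. Neither does the MRI outcome.

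**2. Inputs for an illustration of size**

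From Sample size calculation: mean (SD) MIO improvement 6.09 (7.05), 6.7 (5.25) and 18.5 (2.1) mm for Levels I, II and III; SD 4.8 mm; 10 joints per group; alpha 5%. The 4.8 is the plain average of the three SDs: (7.05 + 5.25 + 2.1)/3 = 4.8. The root-mean-square value is √[(7.05² + 5.25² + 2.1²)/3] = 5.22. The stated minimum of 9 per group is not used here; the number analysed is taken as 10.

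Assumed, because the documents give no assessor error: a systematic shift of b = 1, 2 or 3 mm in Level III only, with no true difference between arms.

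**3. False-positive rate of the planned ANOVA**

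With k = 3 groups of n = 10, the degrees of freedom are 2 and 27, and the 5% critical value of F is 3.354. For means 0, 0, b, the sum of squared deviations from their average is (2/3)b². The noncentrality is therefore

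λ = n × (2/3) × b² / SD²

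and the rejection probability is P(F′(2, 27, λ) > 3.354), where F′ is the noncentral F.

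| b (mm) | λ, SD 4.8 | Rejection, SD 4.8 | Rejection, SD 5.22 |
|---|---|---|---|
| 0 | 0 | 5% | 5% |
| 1 | 10 × 0.667 × 1/23.04 = 0.289 | 7.0% | 6.7% |
| 2 | 10 × 0.667 × 4/23.04 = 1.157 | 13.6% | 12.2% |
| 3 | 10 × 0.667 × 9/23.04 = 2.604 | 25.7% | 22.3% |

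Simulating the same ANOVA with the three stated SDs kept unequal gives about 12% at 2 mm and 22% at 3 mm.

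**4. Sensitivity to the pattern of bias**

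If the shift were 2 mm per level (0, 2, 4 mm), the sum of squares is 8, λ = 10 × 8/23.04 = 3.47, and the rejection probability is about 33%. The size therefore depends on how the bias is spread across arms, which nobody knows.

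**5. Against the effect the plan expects**

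The expected II–III difference is 18.5 − 6.7 = 11.8 mm. If 3 mm of that were bias, 8.8 mm would remain. With means 6.09, 6.7 and 15.5 and SD 4.8, λ = 24.1 and ANOVA power is about 99%. The expected I–II difference is 6.7 − 6.09 = 0.61 mm, smaller than any of the assumed shifts.

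**The case against.** **Silence is not a statement that assessors are unmasked.** Correct. A reader might infer that the surgeon will measure his or her own patients. The documents do not say so. What stands is that the plan permits it.

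**Clicking may be patient-reported.** This also stands. If so, patient blinding already covers it, so clicking counts as exposed only if an examiner detects it.

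**Masking may not be free.** A reader might infer that a non-operating examiner is available without added staff. The documents describe no staffing, and 30 patients at 3 visits is 90 assessments. That part of the remedy has to be conditional. Coding image files does not depend on it.

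**MRI masking may fail where it matters most.** Materials states of the pins that "The mean degradation period was standardized between 18 and 26 months", so by that figure they are still present at 6 months, and Surgical technique also allows titanium screws. Whether either shows on MRI is an assumption. Nor can one infer that Levels I and II are fully indistinguishable: the technique describes an anterior release and retrodiscal scarring meant to let the disc sit further back, and a reader might recognise this. Masking may be partial, but partial masking is still better than none.

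**The size of bias is chosen, not observed.** True. Pairwise Welch tests with the plan's SDs would give larger II–III figures (about 18% at 2 mm and 34% at 3 mm), but the plan specifies a three-group ANOVA, so the lower figures are the relevant ones for a shift in Level III alone.

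**The direction of bias is unknown.** A reader might infer that it must favour Level III, as the sample-size means do. Yet the plan states a null hypothesis, and its PICO question asks whether Level I does better. Bias towards Level III is plausible but not established.

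**Conclusion.** The concern holds as a gap in the plan. Only patients are masked. MIO, lateral excursion, protrusion, MRI disc position and, if examiner-detected, clicking can all be scored by someone who knows the arm.

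The illustrative size is a rise in the ANOVA false-positive rate from 5% to about 7%, 14% or 26%. This rests on an assumed shift of 1, 2 or 3 mm in Level III alone, no true difference, 10 per group and a common SD of 4.8 mm. At 1 mm the effect is minor.

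A reader might infer that assessor bias could account for the whole Level III advantage the plan anticipates. The figures do not support that: 3 mm is about a quarter of 11.8 mm (3/11.8 = 25%). The risk is greatest if the true differences are much smaller than planned, and for disc position, where no quantitative margin is given at all.

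**What to change.** Extend the Blinding section as follows.

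1. **MRI.** Code the 6-month images, remove the group label and operative information, and have them read in mixed order. Name the reader by role.
2. **Analysis.** Run the ANOVA on groups coded A/B/C, and break the code once the analysis is complete. This is a modest safeguard; no analyst bias has been quantified here.
3. **Range of motion and clicking.** State who records these at 1, 3 and 6 months, and whether clicking is patient-reported or examiner-detected. Where the department can manage it without added staff, use someone who did not operate on that patient and has not seen the operation note. Otherwise state that these assessments are unmasked and interpret them accordingly.

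Items 1 and 2 cost protocol wording and file handling. Treatment, visits and sample size do not change. The cost of item 3 cannot be judged from the documents, hence the alternative of open disclosure. The report should also say that MRI masking may be partial in Level III, where fixation may be visible, and may be imperfect in Level II.
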